Gentle Warriors Academy Healthy Marriage and Responsible Fatherhood Program Evaluation

4/22/2024

Clinicaltrials.gov ID: NCT06899100

Statistical Analysis Plan

1. Data Analysis

Briefly describe the planned approach for data analysis. If an impact analysis is proposed, name the key dependent and independent variables, and describe any methods to minimize Type I error (i.e., finding positive impacts by chance) such as limiting the number of impacts to be analyzed and/or multiple comparison correction. Describe proposed approach(es) for addressing missing data.

Analytic Sample

The study sample includes participants who: 1) gave recorded informed consent to be part of the study, and 2) took both an entrance and exit survey. The analytic sample for particular outcome measure will vary based on missing data.

Outcome measures

For each outcome construct, we have identified the relevant measures from nFORM and the OLLE survey that are theoretically aligned with that construct. We will generate a correlation matrix between items in a given construct to ensure that theoretically related items are also empirically related in our data set. Items that are not strongly correlated with other items in a construct will be removed as necessary. Factor analysis will be used to ensure that all construct items hang together (using an alpha of 0.7 or higher as the threshold).

Once we are confident that all of the items align with a given construct, we will create a composite measure by taking an average of the scores on each non-missing item in the construct. The measure definition matrix below provides information on each proposed outcome. For composite measures, a change score will be calculated between a participant's pre-program composite score and post-program follow-up composite score. For standalone survey items, a change score will be calculated between a participant's pre-survey and follow-up survey responses.

For the sake of consistency and simplicity, parenting and co-parenting analyses will use a participant's youngest child as the focal child.

Construct	Sample	Measure	Data source(s)	Variable Name
Parenting Attitudes (toward children)	Has at least one child age 24 or younger	7 items: frequency of key attitudes (categories, 5-point scale)	nFORM entrance, OLLE follow-up	Copar_Att

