Parenting Behaviors (interaction with children)	Has at least one child age 24 or younger, saw child within past month	Continuous (1 item: hours spent w/children in last 30 days (interval); 1 item: frequency reach out to children (categories, 5-point scale); 7 items: frequency engage in key behaviors (categories, 5-point scale)	nFORM entrance, OLLE follow-up	Par_Beh
Co-parenting behavior	Has at least one child age 24 or younger, saw child within past month	11 items: frequency of agreement with key co-parenting behaviors (interval, 5-point scale)	nFORM entrance, OLLE follow-up	CoPar_Beh
Healthy Partner Behavior(Well-being as a parent)	Has at least one child age 24 or younger	1 item: feelings of being overwhelmed as parent (categories, 4 point scale)	nFORM entrance and exit	Well_being

Data preparation

We plan to clean each individual raw data file before merging nFORM and local evaluation surveys together for analysis in R using nFORM Client ID as the linking variable. Quality checks will include checks for duplicate surveys, incorrectly entered nFORM IDs, missing data, and outliers. We will look at descriptive statistics for our variables of interest to look for missing and outlying data.

Approaches to address missing data

Outcomes

When creating the composite measures for co-parenting and parenting relationships, we will create a composite score by taking the average of multiple individual items. For these measures, our current plan is to use 20% as a threshold for allowable missing items, based on guidance from evaluation technical assistance resources. This plan is contingent on the final distribution of missing data in our data set. With a 20% threshold, if a respondent is missing more than 1 item used for creating the co-parenting construct or more than 2 items for creating the parenting construct, the respondent will be assigned a missing value for that construct. We will not be imputing truly missing values for outcomes. To create a construct score, the average will divide by the number of non-missing values in the construct.

Participants who have not seen their child within the past month will have their parenting behavior responses set to “Never” (1) and will be included in the analytic sample for that outcome.

For outcomes that use single survey items, participants who do not respond to the item on either the pre- or follow-up survey will be excluded from the analytic sample for that outcome.

Assessing non-response bias

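### The confirmatory Parenting Behavior score averages hours in 30 days with eight 5-point items without rescaling, so R1 may become mainly a test of hours

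*SAP*

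**What the plan says.** The measure definition matrix in SAP section 1 lists Par_Beh as one variable: "Continuous (1 item: hours spent w/children in last 30 days (interval); 1 item: frequency reach out to children (categories, 5-point scale", followed by seven more 5-point behavior items. Protocol 8.1 lists the same nine items. Protocol 1.2 classes R1 as confirmatory, and the SAP tests it with a paired t-test on the change score.

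On scoring, Outcome measures says "we will create a composite measure by taking an average of the scores on each non-missing item in the construct", and the missing-data section adds that "the average will divide by the number of non-missing values in the construct". Neither document mentions rescaling, banding, capping or weighting of hours. Data preparation checks for outliers but states no action.

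An item screen comes before scoring. "Items that are not strongly correlated with other items in a construct will be removed as necessary", and factor analysis follows, "using an alpha of 0.7 or higher as the threshold". The score is built "Once we are confident that all of the items align with a given construct".

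On missing items, "our current plan is to use 20% as a threshold for allowable missing items". The SAP makes this provisional on the distribution of missing data. It then sets a construct to missing when a respondent is "missing more than 1 item used for creating the co-parenting construct or more than 2 items for creating the parenting construct".

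**The concern.** Hours over 30 days can run to tens or hundreds, while the other eight items run from 1 to 5. In an unweighted mean, the item with the largest spread dominates. If hours is raw and stays in, R1 is mainly a test of hours, and a real gain in the eight behaviors could be missed when hours does not move.

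The screen does not settle whether hours stays. No cut-off defines a strong correlation, removal is discretionary, and the SAP does not say whether raw or standardised alpha must reach 0.7. Correlations and standardised alpha ignore scale and can keep hours; raw alpha tends to reject it. If hours is dropped, R1 tests an outcome other than the one listed, chosen after the data are seen.

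The missing-item rule adds a second problem. A father may lack the hours item at one wave only, and his two scores are then on different scales. If such missingness differs between waves, the mean change is biased. Equal missingness cannot be assumed: baseline comes from nFORM and follow-up from OLLE, and the one-year survey is by web link or phone (Protocol 8.3).

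**Working it through.** The documents give no sample size, SD, power or hours distribution for this outcome, so there is no planned figure to reproduce.

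**From the documents alone**

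- Score = (hours + 8 × item mean)/9.
- All eight items up one point: 8/9 = 0.89, the same as 8 more hours. All eight from 1 to 5: 32/9 = 3.56, the same as 32 more hours.
- A father at 40 hours with every item at 3 scores (40 + 24)/9 = 7.11. With hours missing, the same father scores 24/8 = 3.00, a false change of 4.11.
- Missing-item limits: 20% of 9 parenting-behavior items is 1.8, so one may be missing, but the text allows two (2/9 = 22.2%). 20% of 11 co-parenting items is 2.2, so two may be missing (18.2%), but the text allows one (9.1%). Rounding down gives 1 and 2, to nearest 2 and 2, up 2 and 3. None gives the written 2 and 1. Reading the parenting construct as the seven attitude items (1.4) does not help: a limit of 2 then needs rounding up, which makes co-parenting 3.

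**Assumed inputs:** item SD 1.2, inter-item r 0.4, item–hours r 0.3, n = 200, test–retest correlation 0.6, two-sided 5% test.

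- Var(sum of 8 items) = 8 × 1.44 + 56 × 0.4 × 1.44 = 43.8
- Cov = Cov(hours, sum of 8) = 8 × 0.3 × 1.2 × SD = 2.88 × SD
- Total = SD² + 43.8 + 2 Cov
- R² of score with hours = (SD² + Cov)²/(SD² × Total)
- Raw alpha = 9/8 × [1 − (SD² + 11.52)/Total]
- SD of change = √(0.8 × Total) on the sum scale. A gain of 0.3 on all eight items adds 2.4 to the sum. Power is from the noncentral t.

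Example at SD 25: Cov = 72 and Total = 625 + 43.8 + 144 = 812.8. Then R² = 697²/(625 × 812.8) = 0.96, and the standardised effect is 2.4/√(0.8 × 812.8) = 0.094.

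| Hours SD | R² with hours | Raw alpha | Power, hours unchanged |
|---|---|---|---|
| 5 | 0.64 | 0.70 | 97% |
| 10 | 0.82 | 0.50 | 76% |
| 25 | 0.96 | 0.24 | 26% |
| 50 | 0.99 | 0.13 | 11% |

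The eight-item mean and the z-scored nine-item mean both have power above 99%.

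*Screen.* The mean inter-item correlation is (28 × 0.4 + 8 × 0.3)/36 = 0.378, so standardised alpha is 9 × 0.378/(1 + 8 × 0.378) = 0.85, which passes at any hours SD. Raw alpha falls below 0.70 once the hours SD exceeds about 5.

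*Sensitivity.*

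- Item–hours r of 0.4: power 72%, 25% and 11% at SD 10, 25 and 50.
- SD 25 with n = 100 or 400: 15% or 47%.
- SD 50 with hours rising by 5, 10 or 12.5: 59%, 96% or 99%.
- Banded hours (SD 1 to 2): hours carries 8% to 16% of the score variance, and power is above 99%.

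**Hours missing, no true change** (simulation: 2,000 samples of 200, gamma-distributed hours with mean 50, item mean 3.5). Rejection rates of the nominal 5% test:

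| Missing at follow-up v baseline | Hours SD 50 | Hours SD 25 |
|---|---|---|
| 5% v 5% | 5% | 5% |
| 8% v 5% | 7% | 10% |
| 10% v 5% | 9% | 18% |
| 10% v 0% (worst case) | 25% | 60% |
| 10% v 0%, change from items present at both waves | 5% | 6% |

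For fathers with no contact, coding *Never* (1) as 1 hour instead of 0 shifts the score by only 1/9 = 0.11.

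**The case against.** The power loss needs several conditions that the documents do not establish: hours recorded raw, an SD well above 5, survival of the screen, and no mean change in hours while all eight items improve. The matrix's word *interval* does not settle the format, because it is also applied to the 5-point co-parenting items. The *Never* (1) recode suggests a score thought of as running from 1 to 5. The screen has an alpha of 0.7 and was announced in advance. It uses inter-item correlations and not the pre–post change, and it may well drop hours: an r of 0.3 is hard to call strong. Protocol section 2 expects contact with children to increase, which makes unchanged hours a selective scenario. The missingness rates are assumed, and the SAP calls its threshold provisional.

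Much of this stands as a limit on size. The large losses do need a screen based on correlations or standardised alpha, and the power and rejection figures are illustrative. It does not remove the defect. Hours is the only Par_Beh item listed without a number of scale points, and no text rescales it. Dropping it would change a confirmatory outcome under a rule with no cut-off. A provisional threshold still cannot agree with both written counts.

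**Conclusion.** The concern holds, and should be fixed before analysis. As written, Par_Beh is an unscaled mean of hours and eight 5-point items, and the screen does not determine whether hours stays. If raw hours stays in and does not change, power for a 0.3-point gain on all eight items falls from above 99% to 76%, 26% or 11% at an hours SD of 10, 25 or 50, under the assumed correlations and n = 200. If hours rises as well, the loss is smaller or absent; if hours is banded, the scale problem largely goes away. Unequal missingness of hours can raise false rejection from 5% to between 7% and 18% in the moderate cases examined. The contradiction between the 20% rule and the item counts needs no assumptions. Confidence in the practical impact is medium, because the response format of the hours item is not in the documents.

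**What to change.** Before analysis, define Par_Beh as the mean of the eight 5-point items and report hours as a separate R1 outcome, either labelled exploratory or included in the multiplicity adjustment. Alternatively, z-score all nine items with the baseline mean and SD, using the same constants at both waves.

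In either case:

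- compute each father's change only from items present at both waves;
- reconcile the 20% threshold with the written item counts for both constructs;
- state whether hours is recorded raw or in bands, and which alpha applies;
- state that the *Never* (1) recode applies to the frequency items, and give the hours value for no contact separately.

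The cost is a few SAP sentences and a line of code, with no new data. The downside is one extra reported outcome, or a score expressed in SD units.

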1. RESEARCH QUESTIONS

1.1. OVERVIEW OF RESEARCH QUESTIONS

Please state the research question(s) that the evaluation intends to answer and for each research question indicate the type: implementation or outcome.

- *Implementation Questions: Identifying whether a program has been successful in attaining desired implementation goals (e.g., reaching intended target population, enrolling intended number of participants, delivering training and services in manner intended, etc.)*
- *Outcome Questions: Identifying whether program is associated with intended outcomes for participants (e.g., do participants' knowledge, attitudes, behaviors, or awareness change?)*

Research questions in this study are framed by a Descriptive Evaluation Design to assess whether outcomes improve for low-income fathers who participate in the Gentle Warriors Academy (GWA) Project. Primary outcomes are assessed before and after participants complete core curricula—*Next Level Fatherhood*—and *Case Management* and *Certified Life Coaching* as support services (pre to post). Primary outcomes will indicate whether behavior improved for healthy family relationships (parent, co-parent, and partner). See Table 1 below.

No	Research Question	Implementation or Outcome?
R1	Will participants report significantly healthier parenting behavior after completing primary educational services and employment support services?	Primary Outcome
R2	Will participants report significantly healthier parenting attitudes after completing primary educational services and employment support services?	Primary Outcome

R3	Will participants report significantly healthier co-parenting behavior after completing primary educational services and employment support services?	Primary Outcome
R4	Will participants report significantly healthier partner relationship behavior after completing primary educational services and employment support services?	Primary Outcome

* you may add rows by hitting the tab button, or right click and select insert row below

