1.2. OUTCOME RESEARCH QUESTIONS

For each outcome research question listed above, whether a descriptive or impact design, summarize the inputs (e.g., program components, program supports, implementation features, etc.), target population (e.g., the population for which the effect will be estimated) and the outcomes (e.g., child well-being, father-child engagement, etc.) that will be examined to answer the research question(s). Comparisons for descriptive evaluations may reflect circumstances before the grant, pre-treatment, or pre-determined benchmark from other studies with similar interventions.

Research Question Number Should correspond to the number indicated in Table 1.1 above	Intervention Program component or set of activities that the evaluation will test or examine	Target Population Population for which the effect of the treatment will be estimated	Comparison What the intervention will be compared to (e.g., pre-intervention for descriptive designs)	Outcome Changes that are expected to occur as a result of the intervention	Confirmatory or Exploratory? Confirmatory: those upon which conclusions will be drawn Exploratory: those that may provide additional suggestive evidence
R1	Primary curricula (Next Level Fatherhood); Support Services (Case Management, Life Coaching);	Urban fathers who are 18+ years with children up to 24 years	Assessment of healthy parenting behavior at GWA Project enrollment.	Participants who complete primary and support services will report healthier parenting behavior	Confirmatory

	Continuous Quality Improvement (CQI) Process			one year after GWA Project enrollment.	
R2	Primary curricula (Next Level Fatherhood); Support Services (Case Management, Life Coaching); Continuous Quality Improvement (CQI) Process	Urban fathers who are 18+ years with children up to 24 years	Assessment of healthy parenting attitudes at GWA Project enrollment.	Participants who complete primary and support services will report healthier parenting attitudes one year after GWA Project enrollment.	Confirmatory

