R3	Primary curricula (Next Level Fatherhood); Support Services (Case Management, Life Coaching); Continuous Quality Improvement (CQI) Process	Urban fathers who are 18+ years with children up to 24 years	Assessment of healthy co-parenting behavior at GWA Project enrollment.	Participants who complete primary and support services will report healthier co-parenting behavior one year after GWA Project enrollment.	Confirmatory
R4	Primary curricula (Next Level Fatherhood); Support Services (Case Management, Life Coaching); Continuous Quality	Urban fathers who are 18+ years with children up to 24 years	Assessment of healthy partner relationship behavior at GWA Project enrollment	Participants who complete primary and support services will report healthier partner relationship behavior one year after GWA	Confirmatory

Improvement (CQI) Process	Project enrollment.
---------------------------	---------------------

* you may add rows by hitting the tab button, or right click and select insert row below

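### R4, a confirmatory question on partner relationships, is given only one item on feeling overwhelmed as a parent, so as described its test cannot answer R4

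*SAP*

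**What the plan says.** Protocol 1.1 poses R4 as a primary outcome question: "Will participants report significantly healthier partner relationship behavior". Protocol 1.2 marks R4 as confirmatory and explains the term: "Confirmatory: those upon which conclusions will be drawn". The R4 comparison is "Assessment of healthy partner relationship behavior at GWA Project enrollment", and the expected result is that participants who complete services "will report healthier partner relationship behavior one year after GWA" Project enrollment.

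Protocol 8.1 and the SAP measure definition matrix each have one row with *partner* in its name. In both, the measure is "1 item: feelings of being overwhelmed as parent (categories, 4 point scale". The SAP labels the row "Healthy Partner Behavior(Well-being as a parent", names the variable Well_being, and requires of the sample only a child aged 24 or younger. The instrument reference in Protocol 8.1 is B3 – B3a.

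The SAP takes this row from "nFORM entrance and exit". The other three rows use "nFORM entrance, OLLE follow-up".

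**The concern.** A confirmatory outcome should measure what its question asks. R4 asks how fathers behave toward a partner. The item described asks how burdened a father feels in raising children. A father can feel less overwhelmed with no change in a partner relationship, or with no partner at all, and a relationship can improve while parental strain does not.

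If the plan is followed as described, the R4 test will yield a p-value about parental strain. If the construct name is carried into the report, that result could be read as evidence on partner relationships, which Protocol section 2 (Background) gives as the reason practitioners should be interested in R4. The SAP's internal checks would not catch this. The item correlations and the alpha threshold of 0.7 apply to multi-item constructs, and this row has one item.

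The data source raises a second, lesser question: which wave supplies the later value for this row.

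**Working it through.** No sample size, power or error-rate figure is in dispute. The check follows R4 from question to measure to wave.

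**Step 1: which row belongs to R4.** Neither Protocol 8.1 nor the SAP matrix cites R4 by number, so the link is by construct name. Parenting behavior matches R1, parenting attitudes R2 and co-parenting behavior R3. The remaining row, Healthy Partner Behavior, is the only candidate for R4. If it is not the R4 measure, R4 has none described.

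**Step 2: question against measure.**

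| | R4 (Protocol 1.1 and 1.2) | Matching row (Protocol 8.1, SAP matrix) |
|---|---|---|
| Subject | Partner relationship behavior | Feeling overwhelmed as a parent |
| SAP gloss and variable | – | Well-being as a parent; Well_being |
| SAP sample condition | – | Has a child aged 24 or younger; no partner condition |

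The item text, gloss, variable name and sample column of the SAP row all point to parental well-being. The variable name is the weakest of these, because the same matrix gives the parenting attitudes row the name Copar_Att. Protocol 1.1 treats parent, co-parent and partner as separate domains, so the co-parenting items serve R3 and cannot stand in for R4. Affected: 1 of 4 confirmatory questions.

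**Step 3: instrument references against item counts (Protocol 8.1).**

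| Row | Reference | Labels | Items stated |
|---|---|---|---|
| Parenting attitudes | A3 a–g | 7 | 7 |
| Parenting behavior | A2b, A2c, A5b b–d and f–i | 1 + 1 + 3 + 4 = 9 | 1 + 1 + 7 = 9 |
| Co-parenting | A13 a–k | 11 | 11 |
| Healthy Partner Behavior | B3 – B3a | 2 | 1 |

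Three references match their counts exactly. The fourth does not, and it is the only one outside survey section A. B3a may be a sub-question, or the reference may be to different items from those described. The survey is not supplied, so this cannot be settled from the documents.

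**Step 4: the wave.** I read exit as the nFORM post-program survey. Protocol 8.4 places that survey in the last workshop session, and Protocol 8.3 puts the session about 13 weeks after enrollment. The only one-year instrument in Protocol 8.3 is the OLLE follow-up survey, which this row does not list.

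- *Pointing to one year or the follow-up survey:* the R4 row in Protocol 1.2; the SAP rule for standalone items; the SAP missing-data rule for single items; the horizon in the SAP analytic approach. This is the only single-item outcome, so both item rules apply directly to it.
- *Fitting entrance to exit:* the pre-to-post wording in Protocol 1.1 and section 4 (Research Design); the SAP analytic sample rule, which requires an entrance and an exit survey.

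If one year governs, the listed source stops about 52 − 13 = 39 weeks early. If pre to post governs, the source is adequate and the one-year statements are wrong for this row.

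**The case against.** The strongest reply is that the fault may lie only in the description. The mismatch between B3 – B3a and the stated single item is a concrete sign that the reference may be right and the wording wrong. In that case partner items may have been collected and R4 may be answerable. This stands. A reader might infer that no partner-relationship data exist and that R4 is lost whatever is done. The documents do not support that, because the content of B3 – B3a and of the OLLE surveys is not given. Against a simple slip, the same item text appears in both documents, and the SAP gloss and sample column agree with it. Either way a correction is needed.

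A reader might also infer that a one-year value for this item does not exist. That would rest on one matrix cell that omits OLLE. Nothing says that the OLLE follow-up lacks the item, and several passages fit an entrance-to-exit analysis. The wave conflict is real, but it is a matter for reconciliation and does not show that data are missing.

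Finally, the SAP prints the well-being gloss and the item text in the same row, which lowers the risk of misreporting. It does not supply a measure for R4.

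**Conclusion.** The point holds for the plan as described. One of four confirmatory questions, R4, is matched only to a single 4-point item on feeling overwhelmed as a parent, and change in that item cannot support a conclusion on partner relationship behavior. This must be fixed before outcome analysis.

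The conclusion rests on two assumptions: that the Healthy Partner Behavior row is meant for R4, and that the item wording in the two documents is taken at face value. What is established is that question and described measure do not match, so one of them, or the description, is wrong.

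The source conflict is secondary and the severity does not depend on it. While it stands, the later time point for this row is undefined.

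**What to change.** 1. Check first what B3 – B3a and the OLLE surveys contain.
2. If partner-relationship items were collected at baseline and at the R4 time point, correct the measure description, gloss, variable name and sample (fathers with a partner) in Protocol 8.1 and the SAP matrix. Do this by a dated amendment before outcome analysis, and state whether R4 outcome data had already been seen. The statement matters because Protocol section 5 has the CQI team reviewing nFORM and local evaluation data every two weeks, although the examples listed in Protocol 8.4 are operational.
3. If such items were not collected, label the row as parental well-being and do not use it as evidence on partner relationship behavior. State that R4 will not be answered, and remove it from the confirmatory set and from the p-value adjustment. Report any parental well-being analysis as exploratory and disclose it as a change.
4. Name one wave for this row, and make these places agree: Protocol 1.1, the R4 row of Protocol 1.2, and Protocol section 4; and in the SAP, the analytic sample rule, standalone-item rule, matrix data source, single-item missing-data rule and analytic approach.

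The cost is wording plus an item check, with no new data collection. One confirmatory claim may be lost. A measure named this late carries some selection risk, which disclosure reduces but does not remove. Restricting to partnered fathers shrinks the sample by an amount the documents do not give.

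### The 20% missing-item limit for the confirmatory composites is left open until the final missing-data pattern is known, with nothing separating that choice from the results

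*SAP*

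**What the plan says.** Under the missing-data heading for outcomes, the SAP says that "our current plan is to use 20% as a threshold for allowable missing items", citing technical-assistance guidance. The next sentence makes this provisional: "This plan is contingent on the final distribution of missing data in our data set". It then turns 20% into item counts. A construct score is set to missing "if a respondent is missing more than 1 item used for creating the co-parenting construct", or "more than 2 items for creating the parenting construct". Outcomes are not imputed, and the composite is the mean of the items answered.

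The SAP's measure table lists 11 co-parenting items, 9 parenting-behavior items (1 + 1 + 7) and 7 parenting-attitude items. Partner behavior is one item. The missing-item paragraph names co-parenting and parenting, and does not say whether parenting includes the attitudes composite.

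Under its analytic approach, the SAP runs a paired t-test on each outcome's own analytic sample and adjusts p-values for multiple hypotheses. Protocol section 1.2 labels R1 to R4 confirmatory and defines the term as "Confirmatory: those upon which conclusions will be drawn".

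**The concern.** The missing-item limit is a sample-selection rule. A father over the limit at either wave has no change score and drops out of the test, so moving the limit changes who is analysed.

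The final missing-data distribution is known only when both waves are in hand, and whoever holds it also holds the outcomes. There is one group, so there is no allocation to mask. The SAP's data-preparation step examines descriptive statistics of the outcome variables to look for missing values and outliers, so missingness and outcome distributions are seen together. Protocol section 8.4 has evaluation staff downloading nFORM and OLLE data every two weeks, although for performance monitoring.

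The planned p-value adjustment covers several hypotheses. It does not cover a choice among several samples for one hypothesis. The non-response analysis compares survey completers with non-completers and does not look at item limits. At stake is whether a significant change on a confirmatory composite can be read at its stated error rate.

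**Working it through.** **Step 1. The plan's own item counts.** Allowed missing items = 20% x number of items.

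| Composite | Items | 20% | Floor | Nearest | Ceiling | SAP allows |
|---|---|---|---|---|---|---|
| Co-parenting behavior (R3) | 11 | 2.2 | 2 | 2 | 3 | 1 (1/11 = 9.1%) |
| Parenting behavior (R1) | 9 | 1.8 | 1 | 2 | 2 | 2 (2/9 = 22.2%) |
| Parenting attitudes (R2) | 7 | 1.4 | 1 | 1 | 2 | not stated |

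No rounding rule gives 1 of 11. The count of 2 of 9 needs rounding up and then exceeds 20%. With floor rounding, 1 allowed item fits 5 to 9 items and 2 fits 10 to 14. Keeping the 20% rule therefore does not by itself define one sample.

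**Step 2. How far the limit moves the sample.** The documents give no item-missing rate, so p is assumed: independent across items, and equal at both waves. For k items and a limit of m, the share scored at both waves is [P(X ≤ m)]², with X ~ Binomial(k, p). Example with k = 11, m = 1, p = 0.05: 0.95^11 + 11 x 0.05 x 0.95^10 = 0.898, and 0.898² = 0.807.

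| Items | p | Limit 1 | Limit 2 | Limit 3 |
|---|---|---|---|---|
| 9 | 5% | 86.3% | 98.3% | 99.9% |
| 9 | 10% | 60.0% | 89.7% | 98.3% |
| 11 | 5% | 80.7% | 97.0% | 99.7% |
| 11 | 10% | 48.6% | 82.9% | 96.3% |

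At 10% missingness, one item more or less moves about a third of the co-parenting sample (82.9 - 48.6 = 34.3 points).

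**Step 3. False-positive rate.** The documents give no sample size, significance level or missing rate, so all are assumed. Data were simulated with no true change and missingness unrelated to scores: 200 pairs, 9 or 11 items, and mean item missingness of 5-20%. Missingness was either concentrated in some fathers (beta-distributed) or independent across items. The test was a two-sided paired t-test at 0.05, with 3,000 to 4,000 runs per scenario. Monte Carlo standard error near 5% is √(0.05 x 0.95 / 3,000) = 0.4 points.

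| How the limit is set | Rejection rate |
|---|---|
| One fixed limit | about 5% |
| Chosen on missingness only (for example, the tightest of 1-4 that keeps 85% of fathers) | 4.3-5.7% |
| Better p-value of limits 1 and 2 | roughly 6-9% |
| Best p-value of limits 0, 1, 2 and 4 | roughly 8-14% |

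The second row is the stated criterion followed honestly. The last two rows arise only if results guide the choice. Limits 1 and 2 are the two counts that the SAP itself uses. The four-limit search spans 0% to 44% missing on 9 items (4/9) and is a worst case.

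**The case against.** The strongest reply is that the text ties any change to missing data and not to results. Row two of the last table shows that a change made on that basis costs nothing in type I error when missingness is unrelated to change. This stands. A reader might infer that the plan permits choosing sample and result together, or that the composites' nominal p-values already fail. The documents support neither: they leave an opening, and the p-values fail only if someone departs from the stated criterion.

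A reader might also infer that the intended sample cannot be known. That goes too far. The SAP gives a default of 20%, its source, item counts, the action when the limit is exceeded and the denominator, so a departure could be noticed. What stays unclear is the match between the counts and 20%, and the coverage of the attitudes composite.

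It is also fair to say that flexibility is prudent if missingness turns out heavy, and that a few points of worst-case error matter less than the lack of a comparison group. The first need is met by sensitivity analyses. The second limits the weight of the point but does not remove it, because the plan tests significance, adjusts p-values and calls these outcomes confirmatory.

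**Conclusion.** The concern holds as an unguarded opening, not as a demonstrated bias. The primary rule for R1 and R3 can move once the final data are in, by an unspecified amount, and no provision keeps that decision away from the outcomes. R2 is affected if the attitudes composite falls under the paragraph. R4 has no item limit to move.

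The realistic excess is about 1 to 4 percentage points over 5% (6-9% for the two counts the SAP uses), and about 3 to 9 points in the worst case (8-14%). Both rest on assumed sample size, missing rates and significance level, and on selection by p-value. The effect on who is analysed can be much larger, as step 2 shows. If missingness is related to change, moving the limit could also shift the estimate. The documents give no basis for sizing that.

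**What to change.** 1. Delete the contingency sentence.
2. Lock one 20% limit as primary for each multi-item composite, stating whether attitudes are included, before follow-up outcomes are analysed.
3. Write the limit as item counts that agree with 20%. With floor rounding these are 2 of 11, 1 of 9 and 1 of 7.
4. Because the SAP allows weakly correlated items to be removed, tie the counts to the final item list by a rule fixed now: 1 allowed for 5 to 9 items, 2 for 10 to 14.
5. Report any other limit, such as complete items only, as a named sensitivity analysis.

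No new data are needed. The SAP is dated 4/22/2024, and the protocol's timeline runs follow-up collection to 8/15/2025, so at the SAP date there was room to lock the rule before the final data.

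The cost is a possibly smaller primary sample if item missingness is heavy. Under the step 2 assumptions, going from 2 to 1 allowed item of 9 lowers the scored share from 98.3% to 86.3% at 5% missingness, and from 89.7% to 60.0% at 10%. For co-parenting, going from 1 to 2 of 11 raises it from 80.7% to 97.0%, and from 48.6% to 82.9%.
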